### **7.2.10.2 Reporting to IRB**

The Sponsor-Investigator or designee must report events to the Fred Hutch IRB in accordance with the policies of the IRB.

## **7.2.11 FDA Reporting Requirements**

All Adverse Events will be reported by the Sponsor-Investigator to regulatory authorities, IRB/IECs and investigators in accordance with all applicable global laws and regulations.

**Neoadjuvant aMVAC+Pembrolizumab – non-UC MIBC Protocol**

Consortium Study No.: RG1006206  
Version 8: 20-DEC-2023

**Table 6. Evaluating Adverse Events**

An Investigator who is a qualified physician, will evaluate all adverse events as to CTCAE v5.0.

V5.0 CTCAE Grading	Grade 1	Mild; asymptomatic or mild symptoms; clinical or diagnostic observations only; intervention not indicated.
	Grade 2	Moderate; minimal, local or noninvasive intervention indicated; limiting age-appropriate instrumental ADL.
	Grade 3	Severe or medically significant but not immediately life-threatening; hospitalization or prolongation of hospitalization indicated; disabling; limiting self-care ADL.
	Grade 4	Life threatening consequences; urgent intervention indicated.
	Grade 5	Death related to AE
Seriousness	A serious adverse event is any adverse event occurring at any dose or during any use of Merck product that:	
	† Results in death; or	
	† Is life threatening; or places the participant, in the view of the investigator, at immediate risk of death from the event as it occurred (Note: This does not include an adverse event that, had it occurred in a more severe form, might have caused death.); or	
	† Results in a persistent or significant disability/incapacity (substantial disruption of one's ability to conduct normal life functions); or	
	† Results in or prolongs an existing inpatient hospitalization (hospitalization is defined as an inpatient admission, regardless of length of stay, even if the hospitalization is a precautionary measure for continued observation. (Note: Hospitalization for an elective procedure to treat a pre-existing condition that has not worsened is not a serious adverse event. A pre-existing condition is a clinical condition that is diagnosed prior to the use of a Merck product and is documented in the patient's medical history.); or	
	† Is a congenital anomaly/birth defect (in offspring of participant taking the product regardless of time to diagnosis); or	
	Is a new cancer (that is not a condition of the study) (although not serious per ICH definition, is reportable within 24 hours and to Merck within 2 working days to meet certain local requirements); or	
	Is an overdose (whether accidental or intentional). Any adverse event associated with an overdose is considered a serious adverse event for collection purposes. An overdose that is not associated with an adverse event is considered a non-serious event of clinical interest and must be reported to Merck within 2 working days.	

**Neoadjuvant aMVAC+Pembrolizumab – non-UC MIBC Protocol**

Consortium Study No.: RG1006206

Version 8: 20-DEC-2023

	Other important medical events that may not result in death, not be life threatening, or not require hospitalization may be considered a serious adverse event when, based upon appropriate medical judgment, the event may jeopardize the participant and may require medical or surgical intervention to prevent one of the outcomes listed previously (designated above by a †).
Duration	Record the start and stop dates of the adverse event. If less than 1 day, indicate the appropriate length of time and units
Action taken	Did the adverse event cause Merck product to be discontinued?
Relationship to Merck Product	Did Merck product cause the adverse event? The determination of the likelihood that Merck product caused the adverse event will be provided by an Investigator who is a qualified physician. The investigator's signed/dated initials on the source document or worksheet that supports the causality noted on the AE form, ensures that a medically qualified assessment of causality was done. This initialed document must be retained for the required regulatory time frame. The criteria below are intended as reference guidelines to assist the Investigator in assessing the likelihood of a relationship between the test drug and the adverse event based upon the available information.  The following components are to be used to assess the relationship between Merck product and the AE; the greater the correlation with the components and their respective elements (in number and/or intensity), the more likely Merck product caused the adverse event (AE):
Exposure	Is there evidence that the participant was actually exposed to Merck product such as: reliable history, acceptable compliance assessment (pill count, diary, etc.), expected pharmacologic effect, or measurement of drug/metabolite in bodily specimen?
Time Course	Did the AE follow in a reasonable temporal sequence from administration of Merck product? Is the time of onset of the AE compatible with a drug-induced effect (applies to trials with investigational medicinal product)?
Likely Cause	Is the AE not reasonably explained by another etiology such as underlying disease, other drug(s)/vaccine(s), or other host or environmental factors

## Neoadjuvant aMVAC+Pembrolizumab – non-UC MIBC Protocol

Consortium Study No.: RG1006206

Version 8: 20-DEC-2023

Relationship to Merck Product (continued)	The following components are to be used to assess the relationship between the test drug and the AE: (continued)	
	Dechallenge	
Was Merck product discontinued or dose/exposure/frequency reduced?
 
If yes, did the AE resolve or improve?
 
If yes, this is a positive dechallenge. If no, this is a negative dechallenge.
 
(Note: This criterion is not applicable if: (1) the AE resulted in death or permanent disability; (2) the AE resolved/improved despite continuation of the product; or (3) the trial is a single-dose drug trial); or (4) Merck's product(s) is/are only used one time.)

	Rechallenge	
Was the participant re-exposed to Merck product in this study?
 
If yes, did the AE recur or worsen?
 
If yes, this is a positive rechallenge. If no, this is a negative rechallenge.
 
(Note: This criterion is not applicable if: (1) the initial AE resulted in death or permanent disability, or (2) the trial is a single-dose drug trial); or (3) Merck product(s) is/are used only one time).
 
NOTE: IF A RECHALLENGE IS PLANNED FOR AN ADVERSE EVENT WHICH WAS SERIOUS AND WHICH MAY HAVE BEEN CAUSED BY MERCK PRODUCT, OR IF REEXPOSURE TO MERCK PRODUCT POSES ADDITIONAL POTENTIAL SIGNIFICANT RISK TO THE PARTICIPANT, THEN THE RECHALLENGE MUST BE APPROVED IN ADVANCE BY THE SPONSOR-INVESTIGATOR AS PER DOSE MODIFICATION GUIDELINES IN THE PROTOCOL.

	Consistency with Trial Treatment Profile	Is the clinical/pathological presentation of the AE consistent with previous knowledge regarding Merck product or drug class pharmacology or toxicology?
The assessment of relationship will be reported on the case report forms /worksheets by an Investigator who is a qualified physician according to his/her best clinical judgment, including consideration of the above elements.		
Record one of the following		Use the following scale of criteria as guidance (not all criteria must be present to be indicative of Merck product relationship).
Yes, there is a reasonable possibility of Merck product relationship.		There is evidence of exposure to Merck product. The temporal sequence of the AE onset relative to the administration of Merck product is reasonable. The AE is more likely explained by Merck product than by another cause.
No, there is not a reasonable possibility of Merck product relationship		Participant did not receive the Merck product OR temporal sequence of the AE onset relative to administration of Merck product is not reasonable OR the AE is more likely explained by another cause than the Merck product. (Also entered for a participant with overdose without an associated AE).

## 8.0 STATISTICAL CONSIDERATIONS

The primary objective is to evaluate the pCR rate at RC with neoadjuvant aMVAC and pembrolizumab in non-UC predominant histologic variants. A pCR rate of 8% or less would be considered of insufficient activity based on historical data for TURBT alone. A design with 91% exact power to rule out an 8% pCR rate at the 1-sided 4% exact level, if the true pCR rate is 36% would require 17 patients. The observation of at least 4 patients with pCR (23.5% pCR rate) would be considered evidence to rule out a pCR rate of 8%. The calculations are based on the one-arm binomial calculator at [www.swogstat.org](http://www.swogstat.org).

The anticipated duration of accrual is 17-26 months (1 patient every 30-45 days) given low prevalence (10-25%) of non-UC predominant histologic variants. However, if after the study has been active for 18 months and 8 or fewer patients have been enrolled, the accrual goal may be modified to target a total of 14 patients. In this case, the design would have 96% exact power to rule out an 8% pCR rate at the 1-sided 10% exact level, if the true pCR rate is 40%. The observation of at least 3 patients with pCR (21.4% pCR rate) would be considered evidence to rule out a pCR rate of 8%.

Secondary objectives include an evaluation of the frequency and severity of toxicity of the regimen, evaluation of recurrence-free survival at 2 years and TIL density at RC. With 17 patients, binary proportions can be estimated to within 24% with 95% confidence. Any toxicity with true prevalence of 10% or greater is likely to be observed with an 83% chance. The feasibility of the regimen will be evaluated by the percentage of patients able to undergo RC within 10 weeks from end of study therapy. This proportion along with 95% confidence intervals will be evaluated. The relationship (or lack thereof) between any delay of RC beyond 10 weeks and study therapy will be described.

Distributions of time-to-event outcomes will be estimated using the method of Kaplan-Meier. The rates at specified time points will use these estimates and the associated 95% confidence intervals. Continuous outcomes, such as TIL density and PD-L1 expression levels will be summarized by means, medians, and quantiles. Changes in continuous outcomes (such as CD8, TILs) will be evaluated as both absolute and percentage change. Descriptive statistics will also be used when needed.

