## 1.0 TRIAL SUMMARY

Abbreviated Title	Neoadjuvant aMVAC and Pembro for non-UC MIBC
Trial Phase	Pilot trial
Clinical Indication	Neoadjuvant chemoimmunotherapy
Trial Type	Pilot trial
Type of control	None
Route of administration	IV
Trial Blinding	None
Treatment Groups	Single-arm of patients with new diagnosis of non-UC MIBC
Number of trial participants	14-17
Estimated enrollment period	17-26 months
Estimated duration of trial	2-3 years
Duration of Participation	6 weeks of neoadjuvant treatment (up to 2 years follow-up)
Estimated average length of treatment per patient	6 weeks

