### **5.6 Participant Replacement Strategy**

A patient will be replaced if following TURBT and registration into the study, they do not meet any of the following criteria:

- Begin neoadjuvant study therapy within 12 weeks of first TURBT that showed muscularis propria invasion
- Receive at least one study treatment dose (accelerated MVAC or pembrolizumab)
- Predominant or pure non-UC histology in any TURBT meeting criteria outlined in inclusion and exclusion criteria (Section 5.1.1 and 5.1.2).

If a patient withdraws informed consent any time before radical cystectomy (not due to therapy related toxicity or cancer progression), they can be replaced and will not be considered evaluable for efficacy assessment.

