## Neoadjuvant aMVAC+Pembrolizumab – non-UC MIBC Protocol

Consortium Study No.: RG1006206

Version 8: 20-DEC-2023

chemotherapy plus pembrolizumab has also been FDA-approved in metastatic NSCLC, further supporting the safety and feasibility for the combination.

Moreover, recent data showed significant efficacy of anti-PD-1/PD-L1 agents as neoadjuvant immunotherapy in MIBC. The single arm phase II PURE-01 trial enrolled patients with T2-3bN0M0 MIBC regardless of cisplatin eligibility and met its primary endpoint (based on pCR rate). Three doses of pembrolizumab led to pCR (pT0 in intention-to-treat population) in 42% of patients, while most patients with pCR had PD-L1 combined positive score  $\geq 10$ . These results are very encouraging as the pCR with single-agent pembrolizumab appears comparable to 38% pCR with neoadjuvant conventional-dose MVAC, though it warrants investigation in larger randomized trials. Furthermore, in the single-arm phase II ABACUS trial, two doses of neoadjuvant atezolizumab led to pCR 29% in cisplatin-unfit patients with T2-4N0M0 MIBC. pCR included pT0 (24%) and pTcis (6%); primary endpoint was pCR in  $\geq 20\%$  patients. PD-L1 positive status ( $\geq 5\%$  in TILs based on SP142 assay) was noted in almost half of the patients and pCR rates were 38% in PD-L1-positive and 27% in PD-L1-negative tumors. Both studies confirmed the safety of neoadjuvant immunotherapy. Data from the NABUCCO trial further supports the safety of neoadjuvant immunotherapy. In this trial, neoadjuvant combination immune checkpoint inhibitor blockade with nivolumab and anti-CTLA-4 ipilimumab was shown to be safe among the first 24 patients enrolled with 23 of 24 proceeding to cystectomy on schedule; pathologic complete response was 46% in this trial. Finally, NCT02365766 trial is a phase Ib/II study, currently evaluating the combination of neoadjuvant chemotherapy plus pembrolizumab in cisplatin-eligible (cohort I) and ineligible (cohort II) patients with T2-4aN0M0 MIBC. In cohort I, therapy consisted of pembrolizumab plus cisplatin-based chemotherapy, while in cohort II of pembrolizumab plus gemcitabine. Available data from 40 evaluable patients from cohort I demonstrated feasibility and safety of the combination, with 10% (4/40) of patients not proceeding to RC but only one of which due to toxicity.

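### Does the lack of a success count for 15 or 16 evaluable patients leave the primary result undefined?

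*Combined protocol and SAP*

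**What the plan says.** Section 8.0 sets the null value: "A pCR rate of 8% or less would be considered of insufficient activity based on historical data for TURBT alone". For the main design of 17 patients (one-sided exact level 4%, power 91% at a true rate of 36%), the rule is: "The observation of at least 4 patients with pCR (23.5% pCR rate) would be considered evidence to rule out a pCR rate of 8" percent.

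The fallback has a time and a criterion: "if after the study has been active for 18 months and 8 or fewer patients have been enrolled, the accrual goal may be modified", to a total of 14. The text then says that in this case the design has "96% exact power to rule out an 8% pCR rate at the 1-sided 10% exact level, if the true pCR rate is 40" percent, and gives the matching rule: "The observation of at least 3 patients with pCR (21.4% pCR rate) would be considered evidence to rule out a pCR rate of 8" percent.

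Two other places bear on the number analysed. Section 1.0 lists "Number of trial participants" as 14-17. Section 5.6 says of patients who withdraw consent before cystectomy, for reasons other than toxicity or progression, that "they can be replaced and will not be considered evaluable for efficacy assessment".

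**The concern.** The printed counts are tied to exactly 17 and exactly 14 patients, yet the plan's own rules allow 15 or 16 evaluable. Replacement after consent withdrawal is permitted, not required. With 9 or more enrolled at month 18 the fallback is closed, however slow accrual then becomes.

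If the trial ended with 15 or 16 evaluable patients and exactly 3 responses, carrying over the count of 3 would declare success and carrying over the count of 4 would declare failure. The trial is open-label, so a rule left unwritten might be settled with the responses in view. The stake is the primary conclusion: a count of 3 at these sizes has a false-positive rate above both levels the plan states.

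Smaller questions arise in the same paragraph. The switch is worded as optional and is not expressly declared independent of response data. The level rises from 4% to 10% and the alternative from 36% to 40% without a reason given. The precision and toxicity-detection figures are for 17 patients only.

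**Working it through.** **Inputs.** From Section 8.0: null rate 8%; alternatives 36% and 40%; rules of at least 4 of 17 and at least 3 of 14. With X responses among n patients at true rate p, P(X ≥ r) = Σ C(n,k) p^k (1−p)^(n−k), summed over k = r to n.

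**Step 1: the plan's own figures.**
- n = 17, r = 4: level P(X ≥ 4 | 0.08) = 0.0419; power P(X ≥ 4 | 0.36) = 0.9115. The plan says 4% and 91%.
- n = 14, r = 3: level P(X ≥ 3 | 0.08) = 0.0958; power P(X ≥ 3 | 0.40) = 0.9602. The plan says 10% and 96%.

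Both designs reproduce to the rounding used.

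**Step 2: the sizes with no printed count.**

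| n | count | exact level at 8% | power at 36% |
|---|---|---|---|
| 15 | ≥3 | 0.1130 | 0.947 |
| 15 | ≥4 | 0.0273 | 0.847 |
| 16 | ≥3 | 0.1311 | 0.962 |
| 16 | ≥4 | 0.0342 | 0.883 |

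At 15 or 16, a count of 3 exceeds even the 10% level. A count of 4 meets the 4% level. So 4 is the smallest count consistent with either stated level, and it is also the count attached to the design in force when no switch has been made.

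**Step 3: how often it could matter.** The documents give no consent-withdrawal rate. Assume 2.5% to 7.5% per patient, independent and never replaced. The upper end borrows from Section 9.1, where a cited study is reported "with 10% (4/40) of patients not proceeding to RC but only one of which due to toxicity", so 3/40 = 7.5%.
- Chance of 15 or 16 evaluable out of 17: 0.058 + 0.283 = 0.342 at 2.5%; 0.238 + 0.366 = 0.604 at 7.5%.
- Chance of exactly 3 responses: n = 15, 0.0857 at a true rate of 8% and 0.1002 at 36%; n = 16, 0.0970 and 0.0790.
- Joint chance at a true rate of 8%: 0.058 × 0.0857 + 0.283 × 0.0970 = 0.032 (2.5% withdrawal); 0.238 × 0.0857 + 0.366 × 0.0970 = 0.056 (7.5%).
- Joint chance at 36%: 0.058 × 0.1002 + 0.283 × 0.0790 = 0.028; 0.238 × 0.1002 + 0.366 × 0.0790 = 0.053.

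The ambiguous outcome therefore has a chance of about 3% to 6%. That is probably generous, because the cited study's three non-toxicity cases are not described as consent withdrawals and Section 5.6 allows replacement.

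**Step 4: discretion in the switch.** If the choice between designs were made in the most favourable way with the first 8 patients' results known, the type I error would be 0.0958. If success were claimed on either at least 3 of the first 14 or at least 4 of 17, it would be 0.0999. Neither exceeds the 10% already stated.

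**Step 5: the changed alternative.** At 36%, power is 0.9271 for 14 patients (≥3) and 0.9115 for 17 (≥4). Quoting 40% for the fallback conceals no loss.

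**The case for a change.** The strongest argument for a change is that Section 8.0 states its rule as counts and never says that the 4% or 10% level governs other denominators. In an open-label trial, a rule that has to be inferred is weaker than one that is written, and a sentence costs nothing. The argument is sharpest if unreplaced withdrawals took an unswitched 17-patient trial down to 14 evaluable: 3 responses would then pass at 10% (exact 9.6%) and fail at 4%, so the levels alone would not settle it.

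It stands that the sentence is absent and would be harmless. But the condition on the fallback answers even the 14-evaluable case: the count of 3 belongs to a trial whose accrual goal was modified, not to any trial that happens to have 14 evaluable. For the same reason, a table of counts keyed only to the number evaluable would do harm, because it would apply the 3-response rule to an unswitched trial that had shrunk to 14. On the 7.5% assumption, 14 or fewer evaluable out of 17 has a chance of 13%.

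The slow-accrual route carries less weight than it seems. At 9 patients per 18 months (0.5 a month), patients 15, 16 and 17 arrive at months 30, 32 and 34. The 26 months in Section 1.0 is an estimate, though, and no rule closes accrual at that point. The 14-17 range there reads most naturally as the two targets of Section 8.0.

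**Conclusion.** No change is called for. This is a gap in detail that an analyst following the plan would fill in only one sensible way: without the month-18 modification at least 4 responses are needed, and 3/15 (p = 0.113) or 3/16 (p = 0.131) does not rule out 8% at either stated level. Reading it so keeps the exact level at 2.7% or 3.4% and power at 36% at 84.7% or 88.3%, against 91.1% for the full 17. The outcome that would test the point has a chance of roughly 3% to 6%, and that rests on an assumed withdrawal rate with no replacement.

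The remaining items are presentational. The trigger and timing of the switch are stated. Its optional wording cannot take the error above 10%. The figures for 14 patients are one-line calculations: 1.96 × √(0.25/14) = 0.26 for precision, and 1 − 0.9^14 = 0.77 for the chance of seeing a 10% toxicity.

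The conclusion depends on reading the count of 3 as conditional on the modification, which is how the paragraph is built.

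### Do the pCR decision rules break their stated error level, with the 14-patient fallback quietly raising it from 4% to 9.6%?

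*Combined protocol and SAP*

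**What the plan says.** Section 8.0 (Statistical Considerations) sets the null: "A pCR rate of 8% or less would be considered of insufficient activity". It then gives two designs, each with its own level, power, alternative and cut-off.

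- **Main design, 17 patients.** "A design with 91% exact power to rule out an 8% pCR rate" is specified "at the 1-sided 4% exact level, if the true pCR rate is 36% would require 17 patients". The cut-off is at least 4 responders, or 23.5%.
- **Fallback, 14 patients.** If 8 or fewer patients have been enrolled after 18 months, "the accrual goal may be modified to target a total of 14 patients". This version carries its own one-sided level of 10% and its own power of 96%, for an alternative of 40%. Its decision rule reads: "The observation of at least 3 patients with pCR (21.4% pCR rate) would be considered evidence to rule out a pCR rate of 8" percent.

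The Trial Summary (Section 1.0) calls the study a pilot and gives the number of participants as 14-17, so the smaller size is part of the declared plan. Section 10.3 states that the trial is open-label.

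**The concern.** Four features invite suspicion.

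1. The 4% level is called exact, yet at least 4 of 17 gives 4.19%. Read as a strict ceiling of 4.00%, it would force a cut-off of 5, with power of 79% instead of 91%.
2. The fallback asks for a lower observed rate from fewer patients, and its false-positive rate is 9.6%.
3. The two powers are quoted at different alternatives, 36% and 40%, so the fallback's 96% cannot be compared with the main design's 91%.
4. The switch is optional and comes at 18 months in an unblinded single-centre trial, when pCR results for up to 8 patients may be known. The easier rule could be chosen with results in view.

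The primary conclusion would be at stake. If the plan promised 4% and delivered nearly 10%, a claim that 8% is excluded would rest on weaker evidence than readers were told.

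**Working it through.** **Inputs, all from Section 8.0:** null rate 0.08; 17 patients, at least 4 responders, alternative 0.36; 14 patients, at least 3 responders, alternative 0.40. For n patients and cut-off r, the chance of success at true rate p is P(X ≥ r) = 1 − Σ C(n,k) p^k (1−p)^(n−k), summed over k = 0 to r−1.

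**Step 1. Reproduce the stated figures.**

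- Level, ≥4/17 at 8%: 1 − (0.2423 + 0.3582 + 0.2492 + 0.1083) = 0.0419 before rounding of terms. Stated 4%.
- Power, ≥4/17 at 36%: 1 − (0.0005 + 0.0048 + 0.0218 + 0.0614) = 0.9115. Stated 91%.
- Level, ≥3/14 at 8%: 1 − (0.3112 + 0.3788 + 0.2141) = 0.0958 before rounding of terms. Stated 10%.
- Power, ≥3/14 at 40%: 1 − (0.0008 + 0.0073 + 0.0317) = 0.9602. Stated 96%.

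All four agree in whole percents. The 17-patient level exceeds a literal 4.00% by 0.19 points, and the 14-patient level lies inside its stated 10%.

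**Step 2. Does 3/14 exclude 8%?** At the stated one-sided 10% level, the exact (Clopper-Pearson) lower bound is the p that solves P(X ≥ 3 | 14, p) = 0.10, which is 8.15%. So 8% is excluded, as the plan says. The bound of 6.1% that would include 8% belongs to a one-sided 5% level, which the plan does not set for this design.

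**Step 3. Can choosing the rule after seeing results raise the error?** Take a true rate of 8% and suppose all eight results are known at the switch.

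| pCRs in 8 | Probability | Later success, ≥3/14 | Later success, ≥4/17 |
|---|---|---|---|
| 0 | 0.5132 | 0.0085 | 0.0037 |
| 1 | 0.3570 | 0.0773 | 0.0298 |
| 2 | 0.1087 | 0.3936 | 0.1583 |
| 3 | 0.0189 | 1 | 0.5278 |
| 4 or more | 0.0022 | 1 | 1 |

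The 14-patient rule is at least as favourable in every row. A team that always takes the better option therefore always takes that rule, and its overall level is 0.0044 + 0.0276 + 0.0428 + 0.0189 + 0.0022 = 0.0958 after rounding, the same as in Step 1.

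A still looser procedure counts success on at least 3 of the first 14 or at least 4 of 17. It adds two paths: 2 in the first 14 and at least 2 of the next 3 (0.2141 × 0.0182 = 0.0039), and 1 in the first 14 and 3 of the next 3 (0.3788 × 0.0005 = 0.0002). The total is 0.0958 + 0.0039 + 0.0002 = 0.0999. Even this stays within the stated 10%.

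**Step 4. What would a stricter fallback cost?** At least 4 of 14 has level 2.1%, but power at 36% falls from 92.7% to 80.2%, and at 40% from 96.0% to 87.6%.

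**Step 5. The other planning figures.** Section 8.0 ties its precision figure explicitly to 17 patients. The normal half-width is 1.96 × √(0.25/17) = 23.8 points against the stated 24, and the largest exact half-width is 24.6. The chance of seeing a toxicity of 10% prevalence is 1 − 0.9^17 = 83%, as stated. With 14 patients it would be 1 − 0.9^14 = 77% and the largest exact half-width 27.0. The plan's figures are right for the size to which they apply.

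**The case for a change.** The strongest opposing case leaves the 4% label aside. Slow accrual makes a positive conclusion easier to reach. The chance of success under ≥3/14 against ≥4/17 is 9.6% against 4.2% at a true rate of 8%, 35% against 24% at 15%, 55% against 45% at 20%, and 92.7% against 91.1% at 36%. The plan gives no reason for moving the level from 4% to 10% or the alternative from 36% to 40%, and it describes both outcomes in the same words. After 2 pCRs in 8, the chance of a false success is 39% under the smaller rule and 16% under the larger.

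These figures are correct, and the lack of a stated reason is a fair remark. They do not show an error in the plan. The success probabilities are higher because the level is higher, and that level is printed beside the rule. The alternative is printed next to each power, so nobody is led to read 96% as a value at 36%; at that rate the fallback still has 92.7%, above the main design's 91.1%. The 39% and 16% condition on an early result that has a probability of 10.9% at a true rate of 8%. They are not error rates of the trial, and Step 3 already counts that row. The trigger itself is an enrolment count at a fixed time, not an outcome.

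**Conclusion.** The concern does not hold. The plan claims 4% only for the 17-patient rule, whose exact level of 4.19% rounds to it, and it claims 10% for the 14-patient rule, whose exact level is 9.58%. Both powers reproduce, and 3/14 excludes 8% at the level set for it. The optional, unblinded switch cannot take the error above the disclosed 10%: the worst cases are 9.58% and 9.99%.

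A looser level when accrual fails is a design trade-off in a pilot of 14-17 patients. A cut-off of 4 in 14 would lower the level to 2.1% at a cost of 12.5 points of power at 36% (92.7% − 80.2%). Another statistician might choose differently, but nothing in the documents requires 4% for the fallback. More decimals, power at a common alternative, or the 77% figure for 14 patients would be added detail and would correct no mistake.

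This rests on two assumptions: that the whole-percent figures in Section 8.0 are rounded values, as their agreement with the exact results indicates, and that the decision is made on exactly 17 or 14 patients with the stated cut-offs.
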